## 2) Related

For reasons such as the following, the possibility of a relationship between occurrence of an AE and the IMP is reasonably conceivable.

- a) A relationship is predictable from the pharmacological and toxicological effects of the IMP.  
Examples: Occurrence of “pancytopenia” when effects on the hematopoietic system have been observed in non-clinical studies, or the occurrence of “dehydration” when the drug has a diuretic effect.
- b) The event has been observed in previous non-clinical studies and/or clinical studies.  
Example: An AE with high incidences in phase 1 studies.
- c) A temporal relationship is suspected between IMP administration and onset of the AE.  
Example: “Allergic dermatitis” occurring several days after the start of IMP administration.
- d) A relationship is suspected based on the outcome of an AE after discontinuation or dose reduction of the IMP.  
Example: Prompt disappearance of “nausea” after discontinuation of the IMP.
- e) A relationship with the IMP cannot be ruled out for other reasons based on medical consideration.

### **8.3.5 Actions to Be Taken Regarding IMP Administration**

Actions to be taken regarding IMP administration following the occurrence of an AE after initiation of IMP administration will be selected from among the following.

- No change
- Discontinuation of IMP administration
- Interruption of IMP administration
- Unknown
- Not applicable

### **8.3.6 Actions to Be Taken for Adverse Events**

The performance of medical treatments (medications and/or other treatments) for AEs and details of the treatments will be described in the CRF (or in the medical records during the extended treatment part).

### **8.3.7 Outcome**

The outcome of an AE will be selected from the following six categories (one only).

If the subject died, the date of death will be recorded in the CRF (or in the medical records during the extended treatment part); if the subject's condition was recovering/resolving, not recovered/not resolved, or unknown, the date of outcome confirmation will be recorded in the CRF (or in the medical records during the extended treatment part [Cohorts 1, 2, and 4]).

- Recovered/resolved
- Recovering/resolving
- Not recovered/not resolved
- Recovered/resolved with sequelae
- Fatal
- Unknown (for some reason, a follow-up investigation could not be performed even once)

## **8.4 Follow-up Investigation of Adverse Events**

The term "recovered" used below means that a subject who had an AE prior to the start of IMP administration returned to his or her original condition, or a subject who had an AE after the start of IMP administration returned to his or her condition before the start of IMP administration.

- 1) If an AE has not resolved by the end of the withdrawal examination, the investigator or subinvestigator will explain to the subject the need for post-trial follow-up investigation and request the subject's cooperation. The investigator or subinvestigator will conduct a follow-up investigation within 4 weeks after the end of the trial and record information regarding the AE in the subject's medical records. If an AE has not resolved by the end of the withdrawal examination, the investigator or subinvestigator will record the outcome in the CRF as "recovering/resolving," "not recovered/not resolved," or as otherwise appropriate.

- 2) If an AE has not resolved by the day of the follow-up investigation and a causal relationship with the IMP cannot be ruled out, Note follow-up investigation will be continued until the event resolves or becomes stable and information regarding the AE will be recorded in the subject's medical records. If a causal relationship between the AE and the IMP can be ruled out, no further follow-up will be made beyond the day of the initial follow-up investigation.
- 3) If, between the end of the withdrawal examination and the day of the follow-up investigation, a new SAE for which a causal relationship with the IMP cannot be ruled out Note occurs, or if an AE that has not resolved by the end of the withdrawal examination and for which a causal relationship with the IMP cannot be ruled out Note becomes serious, follow-up investigation will be conducted until the AE resolves or becomes stable and information regarding the AE will be recorded in the subject's medical records.
- 4) If an SAE for which a relationship with the IMP cannot be ruled out Note is discovered after the end of the withdrawal examination, or after the day of the initial follow-up investigation (if performed), follow-up investigation will be conducted until the AE resolves or becomes stable or until follow-up of the subject becomes impossible and information regarding the AE will be recorded in the subject's medical records.
- 5) If the treatment for AML is initiated after the end of the withdrawal examination, and it is difficult to confirm the subject's outcome under the influence of the treatment in the opinion of the investigator or subinvestigator, no follow-up investigation of the AE will be performed even if the subject has not recovered from the AE by the end of the withdrawal examination.

Note Including those for which a causal relationship is not determined.

## **8.5 Pregnancy**

If women of childbearing potential or male subjects whose partners are capable of becoming pregnant participate in the trial, the investigator or subinvestigator will attend to the following.

- Information on pregnancy in the written information for subjects and ICF
- Explanation of contraceptive methods
- Reporting and follow-up of cases of pregnancy

### **8.5.1 Guidance to Subjects Including Contraceptive Methods**

- 1) Before the start of the trial, the investigator or subinvestigator will explain to the subjects the importance of using contraception and the risks associated with pregnancy of a female subject or partner of a male subject and, after subjects have read the written information for subjects and understood it, the investigator or subinvestigator will have subjects sign the ICF.
- 2) If women of childbearing potential or male subjects whose partners are capable of becoming pregnant wish to participate in the trial, the investigator or

subinvestigator will instruct them to practice contraception during the period specified in the trial protocol.

- 3) Contraceptive methods include condoms, pills, pessaries, intrauterine device, implantable contraceptive devicesNote, spermicideNote, vasectomy, and tubal ligation. However, if a female subject or male subject's partner is without question unable to become pregnant (ie, has undergone bilateral ovariectomy or hysterectomy or has not experienced menses for at least 12 consecutive months without an alternative medical cause, or the male subject/partner has undergone bilateral orchidectomy), use of contraception is unnecessary.

Note Methods not approved or authorized in Japan.

- 4) The investigator or subinvestigator will instruct the subjects that if the contraceptive measures fail and evidence of pregnancy of the female subject or male subject's partner such as delay in menstruation is observed during the trial, this should be promptly reported to the investigator or subinvestigator.

### **8.5.2 Actions to Be Taken by the Investigator or Subinvestigator When Pregnancy Is Suspected**

If the investigator or subinvestigator or a subject suspects that the subject has become pregnant before initiation of IMP administration, initiation of IMP administration will be withheld and a pregnancy test will be performed. If the test result is positive, the trial subject will be withdrawn without receiving IMP administration. If a pregnancy is suspected after initiation of IMP administration, IMP administration will be discontinued (refer to [Section 9.2](#) Criteria and Procedures for Withdrawal of Individual Subjects).

### **8.5.3 Actions to Be Taken by the Investigator or Subinvestigator When a Subject Is Discovered to Be Pregnant**

When a female subject is found to be pregnant, the investigator or subinvestigator will withdraw the subject from the trial and perform follow-up investigation until delivery or end of pregnancy, and report this in writing to the sponsor.

After discontinuation of IMP administration, the investigator or subinvestigator will perform the withdrawal examinations and follow-up observation stipulated in the protocol, in so far as they do not affect the pregnancy. For example, examinations such as radiography should not be performed even if they are stipulated in the protocol.

### **8.5.4 Expedited Reporting of Pregnancy**

When a female subject or a partner of a male subject is found to be pregnant during the trial, the investigator or subinvestigator will promptly report this to the sponsor in person, by telephone, or by e-mail (refer to Annex 1 Emergency Contact). The investigator or subinvestigator will then provide any additional information requested by the sponsor.

### **8.5.5 Follow-up Investigation of Pregnancy**

If a female subject becomes pregnant, the investigator or subinvestigator will perform follow-up investigation of the pregnancy up to delivery or the end of pregnancy and report the results of follow-up in writing to the sponsor. When a subject or subject's partner has delivered, it is best that the neonate be observed for at least 6 months after delivery.

## **9 Withdrawal of Individual Subjects From the Trial**

Any subject may discontinue participation in the trial at any time without medical disadvantage. The investigator or subinvestigator may withdraw a subject from the trial at any time if it is considered necessary for medical treatment of that subject.

### **9.1 Screen Failure**

If a subject is a screen failure, the following information should be recorded in the CRF for screen failure subjects.

Date of investigation (the start date of the screening examination), date of informed consent acquisition, date of birth, sex, reason for screen failure.

### **9.2 Criteria and Procedures for Withdrawal of Individual Subjects**

In any of the events listed below, the investigator or subinvestigator will withdraw the subject from the trial, perform the tests such as the withdrawal examination stipulated in [Section 7.1](#) Schedule and Procedures, and promptly inform the sponsor of the withdrawal (Annex 1 Emergency Contact). The investigator or subinvestigator will record the date and reason for withdrawal in the CRF.

For subjects who do not undergo the withdrawal examination, the date of withdrawal will be the day when the investigator or subinvestigator deems withdrawal is necessary.

If withdrawal is necessitated by problems with safety, such as the occurrence of an AE or aggravation of the underlying disease, the investigator or subinvestigator will promptly take appropriate measures and perform follow-up if necessary (refer to [Section 8.4](#) Follow-up Investigation of Adverse Events).

- 1) Apparent progression (including the relapse) of the primary disease.
- 2) Dose-limiting toxicity that does not improve to the baseline level or show improvement by at least 1 grade within 4 weeks, or occurrence of another DLT.
- 3) Delay in commencement of the next course by more than 4 weeks due to an AE, unless the investigator or subinvestigator judges that continuation of SGI-110

administration is in the patient's best interest, in which case the delay may be extended by another 2 weeks.

- 4) Subject becomes pregnant.
- 5) Subject wishes to withdraw from the trial.
- 6) The investigator or subinvestigator judges that it is difficult to continue IMP administration due to occurrence of an AE.
- 7) The investigator or subinvestigator judges that it is necessary to discontinue IMP administration for any other reason.

### **9.3 Follow-up Investigation of Subjects Who Do not Visit the Trial Site**

When a subject fails to visit the trial site and the reason is unknown, the investigator or subinvestigator will immediately contact the subject or their family by telephone or other means to confirm whether or not AEs have occurred and encourage the subject to return. If again the subject fails to visit the site after being contacted, the following information should be obtained and recorded in the CRF (or in the medical records during the extended treatment part).

- 1) The date of investigation
- 2) The method of investigation
- 3) Whether or not the subject was contacted
- 4) Reason why the subject does not (or cannot) visit the trial site
- 5) Occurrence or non-occurrence of AEs. If an AE has occurred: name of the event, date of onset and date of recovery, seriousness, severity, relationship to the IMP, measures taken regarding IMP administration, outcome.
- 6) If follow-up investigation is impossible: the reason why

## **10 Collection of Case Report Form Data and Specification of Source Data**

### **10.1 Collection of Case Report Form Data**

- 1) Electronic Data Capture (EDC) will be used in the primary evaluation part of the trial, and the paper CRF will be used in the extended treatment part for data collection.
- 2) Subject data will be entered directly into the database from the trial site via a Web browser. These data collected by EDC will constitute the CRF. The 12-lead ECG analysis results obtained from the ECG reading facility (central ECG reading facility) will be transferred from the ECG measurement facilities directly to the sponsor.
- 3) Regarding quality assurance of CRFs, the guidelines specified in "Use of Electromagnetic Records and Electronic Signatures in Applications for Approval or Licensing of Drugs" (PFSB Notification No. 0401022, dated 01 Apr 2005) and

“Guidance on Electronic Capture of Clinical Study Data” (Drug Evaluation Committee, Japan Pharmaceutical Manufacturers Association, dated 01 Nov 2007) will be observed

- 4) For every subject who provides consent to participate in the trial, a CRF will be created on an EDC data entry screen that conforms to the items of CRF data collection described in the trial protocol.
- 5) The investigator, subinvestigator, or trial associate will create CRFs according to the manual provided by the sponsor. If source documents are available and the objectivity of the data can be ensured, then the data may be recorded in a CRF by a trial associate.
- 6) When entering data into CRFs from the trial site, a predetermined check will be automatically performed. The investigator, subinvestigator, or a trial associate will make corrections as necessary.
- 7) The sponsor will verify CRFs in comparison to source documents and conduct data reviews. If additional query is necessary, the sponsor will issue an intra-system query and the investigator, subinvestigator, or a trial associate will perform data correction or provide a response to the sponsor’s query as necessary.
- 8) A history of all revisions made after the initial data entry is saved on the server will be automatically recorded within the system (date and time of revision, name of person making revision, pre- and post-revision data, reason for revision, date and time of query, name of person issuing query, details of query, etc).
- 9) After completion of all CRF data entry and confirmation that the content is correct and complete, including confirmation of the audit trail, the investigator will attach an electronic signature.
- 10) Details concerning data collection will be specified in a separate manual prepared in advance.

## **10.2 Source Documents**

- 1) Source documents are defined as those documents that are the source of data transcribed into CRFs as trial results.  
Medical records and other records (medical records, nursing records, prescription records), registration verification forms, subject screening list, ICFs, clinical laboratory test and other measurement reports, ECG charts, IMP management records, and other documents
- 2) The investigator or the trial site will retain all trial-related documents and records except CRFs in such a manner that enables the sponsor or the regulatory authority to have direct access to the documents and records.
- 3) The original ICFs will be retained according to the method specified by each trial site.
- 4) After completion of the trial, the sponsor will retain the original CRFs on CD-ROM or some other appropriate electronic medium and the investigator or the trial site will retain copies.
- 5) The original report on results of drug concentration measurement will be kept by the laboratory performing drug concentration measurements, and the original

report on results of PD measurements will be kept by the PD measurement laboratory; copies will be kept by the sponsor.

### **10.3 Case Report Form Items to Be Treated as Source Data**

Of the data recorded in the CRF, the following items will be treated as CRF-based source data.

- Investigator's signature, date of the investigator's confirmation
- Comments presented for each item
- Occurrence or non-occurrence of AEs. If an AE has occurred: name of the event, severity, seriousness, measures taken regarding IMP administration, treatment of AE, outcome, (causal) relationship to the IMP
- Reason for withdrawal
- Response to previous treatment
- Presence or absence, dose and regimen, and reason for use of concomitant drugs
- Presence or absence, details, and reason for implementation of concomitant therapies
- Cause of death found in an investigation on the outcome of survival

### **10.4 Data to Be Collected by the Sponsor**

- 1) CRFs (data following acquisition of informed consent)
- 2) Clinical laboratory results and reference values
- 3) Copies of results of drug concentration measurement
- 4) Copies of results of PD measurement
- 5) Copies of ECG charts
- 6) 12-lead ECG analysis report

## **11 Statistical Analysis**

The analysis sets, endpoints, analysis subjects, analysis methods, and other relevant matters in the primary evaluation part are defined in this section. Planned statistical analyses are detailed in the statistical analysis plan and PK analysis plan prepared separately. The statistical analysis plan and PK analysis plan will be finalized before database lock.

### **11.1 Statistical Analysis Sets**

#### **11.1.1 Safety Analysis Set**

The safety analysis set will include subjects who have received at least one dose of the IMP.

#### **11.1.1.1 Dose-limiting Toxicity Analysis Set**

The DLT analysis set will include subjects in whom tolerability has been assessed in Cohorts 1 to 4 (subjects who have received all doses and completed all assessments scheduled for the DLT evaluation period).

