The sponsor will review safety data obtained from the previous cohort(s) and judge the transition to the next cohort, including selection of a cohort to proceed to, based on the advice of the Independent Data Monitoring Committee.

If the number of subjects exhibiting DLT within a cohort is  $\geq 2/3$  or  $\geq 2/6$ , then there will be no transition to the next cohort, and the MTD will be determined as follows:

$\geq 2/3$ or $\geq 2/6$ subjects with DLT	MTD
In Cohort 1	$< 36 \text{ mg/m}^2$ in 5-day regimen
In Cohort 2	$36 \text{ mg/m}^2$ in 5-day regimen
In Cohort 4	$60 \text{ mg/m}^2$ in 5-day regimen

If the incidence of DLT does not reach either  $\geq 2/3$  or  $\geq 2/6$  in any of the cohorts in the table above, the MTD will not be determined in this study. For Cohort 3 ( $60 \text{ mg/m}^2$  in 10-day regimen), DLT will be evaluated but the MTD of 10-day regimen will not be determined from the incidence of DLT.

The DLT evaluation period will be from the start of administration in Course 1 to the examination scheduled for Day 29 of Course 1. However, for subjects who have postponed the start of IMP administration scheduled for Day 1 of Course 2 (extended treatment period), the DLT evaluation period will last until the start of IMP administration in Course 2.

Subjects will be hospitalized for treatment during Course 1. Subjects will be required to remain hospitalized until the examination scheduled for Day 29 of Course 1 if they complete the trial in Course 1 (until the withdrawal examination if they are withdrawn during Course 1) and until the start of IMP administration in Course 2 if they proceed to the extended treatment period of Course 2 and the subsequent courses.

Dose-limiting toxicity shall be defined as any of the following AEs occurring during Course 1 for which there is a reasonable probability or possibility of a causal relationship with the IMP (being related to the IMP) if it cannot be reasonably explained by underlying disease, intercurrent illness, or concomitant medications. The severity of AEs will be graded in accordance with Common Terminology Criteria for Adverse Events (CTCAE) version 4.0.

- Non-hematologic toxicity of Grade 3 or higher, except for the following:
  - Nausea, vomiting, or diarrhea of Grade 3 that is controllable by optimal therapy

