### 3.5 Rules to Be Observed for Enrollment and Treatment

- 1) The dose or regimen should remain unchanged for each subject, and no subject should be re-enrolled.
- 2) In order to avoid occurrence of unexpected serious adverse drug reactions in multiple subjects, the IMP should be administered to the second subject after the following day of Day 1 of Course 1 in the first subject at each dose level.
- 3) When the administration or examination scheduled for Course 1 cannot be implemented for reasons other than safety, the subject should be excluded from the DLT evaluation, and another subject should be enrolled.
- 4) Administration of SGI-110 is expected to cause myelosuppression and infection (eg, febrile neutropenia, pneumonia, and sepsis). Delay or discontinuation of administration should be determined for subjects who have experienced or are suspected to have experienced pyrexia or infection based on data from laboratory tests, physical examination (body temperature), and imaging tests before the start of the next course and continuing the treatment.
- 5) In and after Course 2 (extended treatment period), IMP administration may be suspended (skipped) from Day 2 and onwards at the discretion of the investigator or subinvestigator, depending on the subject's condition. Subjects who fall under any of the discontinuation criteria should be withdrawn from the trial.

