**7.1.5 Observations, Examinations, and Evaluations at the Time of Withdrawal**

The observations, examinations, and evaluations listed below will be conducted within 5 days after withdrawal from the trial has been decided, and the dates of the conduct and

data obtained will be documented in the medical records and CRF. If the withdrawal examination takes place within the acceptable time window for Day 8, Day 15, Day 22, or Day 29, it is not necessary to repeat items that have been performed in the examinations for Day 8, Day 15, Day 22, or Day 29 for the withdrawal examination. If the withdrawal is due to an SAE or progression of the primary disease, only those examinations that are feasible, given the subject’s state of health, will be performed in consideration of the subject’s conditions.

Clinical Symptoms	Subjective symptoms and objective findings
Pregnancy Test a	Urinary or serum HCG
Vital Signs	Blood pressure (systolic/diastolic), pulse rate, and body temperature
Body Weight	Body weight
Twelve-lead ECG and chest X-ray	Twelve-lead ECG and chest X-ray
Hematology Test	Hb, Hct, RBC count, WBC count, differential WBC count (visual count: blast cells [leukemia cells], lymphoblastoid cells, monoblasts, promyelocytes, myelocytes, metamyelocytes, segmented neutrophils, stab leucocytes, lymphocytes, eosinophils, monocytes, basophils, prolymphocytes, and promonocytes), platelet count, and reticulocytes
Blood Biochemistry Test	AST (GOT), ALT (GPT), ALP, LDH, TP, ALB, T-Bil, BUN, UA, Cr, blood glucose (fasting), Ca, Mg, Na, K, and Cl
Urinalysis	Bilirubin, occult blood, protein, and urobilinogen
General Condition	ECOG PS
Bone Marrow Aspiration b	Percentage of bone marrow fluid (blasts, lymphoblasts, monoblasts, promyelocytes, myelocytes, metamyelocytes, segmented neutrophils, stab leucocytes, lymphocytes, eosinophils, monocytes, basophils, normoblasts, pronormoblasts, erythroblasts, plasma cells, and megakaryocytes), M/E ratio, and cellularity

HCG = Human chorionic gonadotropin

a A pregnancy test will be performed in female subjects at the trial site. However, a pregnancy test is not required for subjects who have undergone bilateral oophorectomy or hysterectomy, or subjects who have been amenorrheic without a medical cause for at least 12 consecutive months.

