### **11.3 Analysis Items and Method**

#### **11.3.1 Safety Analysis**

##### **11.3.1.1 Primary Endpoint**

- 1) Definition  
DLT
- 2) Analysis set  
DLT analysis set

3) Analysis method

Dose-limiting toxicities (by preferred term [PT]) occurring during Course 1 in each cohort will be tabulated (number and percentage of subjects with DLTs).

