9.2 Primary Endpoints

DLT is the primary endpoint of this trial.

DLT evaluation analysis set will be used for the analysis.

- DLTs [preferred term (PT)] which observed on course 1 will be tabulated (number of subjects and incidence rate) by DLT criteria and Medical Dictionary for Regulatory Activities (MedDRA) system organ class (SOC) and PT.

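### The DLT analysis set makes no exception for subjects who had a DLT, so a DLT that cuts Course 1 short drops out of the primary table

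*Protocol*

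**What the plan says.** Protocol 11.1.1.1 describes the DLT analysis set as subjects whose tolerability was assessed, and specifies them in parentheses as "subjects who have received all doses and completed all assessments scheduled for the DLT evaluation period". SAP 5.1.1.1 repeats this. The primary DLT table uses that set: Protocol 11.3.1.1 names it for the count and percentage with a Course 1 DLT by cohort, and SAP 9.2 says "DLT evaluation analysis set will be used for the analysis". SAP section 13, which lists departures from the protocol, adds no exception.

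Protocol 3.5 item 3 covers the same ground differently. When Course 1 dosing or an examination "cannot be implemented for reasons other than safety, the subject should be excluded from the DLT evaluation", and another subject is enrolled. It says nothing about removing a subject whose miss was caused by safety.

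Course 1 can be cut short by toxicity. Protocol 9.2 item 6 withdraws a subject when the investigator "judges that it is difficult to continue IMP administration due to occurrence of an AE". Protocol 7.1.5 reduces what is then collected: "If the withdrawal is due to an SAE or progression of the primary disease, only those examinations that are feasible" are done.

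**The concern.** A completers-only set is a sensible way to decide who counts as free of DLT, because such a subject must have been observed long enough. It is the wrong condition for a subject who has already had a DLT, since the endpoint has been reached and nothing further needs observing. Applied to everyone, the rule makes inclusion depend on the outcome. The primary table can lose subjects with a DLT and can never gain one, and the events most likely to be lost are the severe ones that stop treatment.

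At stake is the reported Course 1 DLT rate in cohorts of 3 to 6, where one subject changes the result materially. The primary table could also disagree with the DLT table on the safety analysis set (SAP 9.3.1) and with the count used for escalation in Protocol 3.1, with nothing in the plan to explain the difference.

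**Working it through.** **Can a subject with a DLT fail the set definition?**

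- *Early withdrawal for an AE.* The DLT definition in Protocol 3.1 includes "Non-hematologic toxicity of Grade 3 or higher, except for the following" (the listed exceptions are certain Grade 3 events). Such an event during dosing can lead to withdrawal under 9.2 item 6 and therefore to missed doses.
- *Missed assessments.* After an SAE, 7.1.5 requires only feasible examinations.
- *Death.* A fatal event is Grade 5 (Protocol 8.3.3), so an IMP-related non-hematologic one meets the DLT definition. The Day 29 window in Table 7.1-1 is Day 26 to Day 32, so a subject who dies before Day 26 cannot complete the Day 29 assessments.

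**How wide are these routes?**

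- A subject with a DLT who completes every dose and assessment stays in.
- A single DLT does not itself force withdrawal. Protocol 9.2 item 2 requires "Dose-limiting toxicity that does not improve to the baseline level or show improvement by at least 1 grade within 4 weeks", or a further DLT.
- Grade 4 cytopenias must last more than 7 days to count. Unresolved febrile neutropenia and a delay of more than 4 weeks are settled only at or after the end of Course 1. In Cohorts 1, 2 and 4, where the last dose is on Day 5, the missed-dose route is therefore mainly an early non-hematologic event. It is wider in Cohort 3, which doses to Day 12 (Protocol 6.1).
- Course 1 is spent in hospital, and withdrawal data falling in a visit window count for that visit (SAP 6.3), so missed assessments should be uncommon.

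**Inputs for the count.** Protocol 3.4 gives at most 6 subjects per cohort (4 × 6 = 24, the stated maximum). Let D be the number of subjects with a DLT among 6 dosed, d the DLT subjects removed by the rule, and k the non-DLT subjects removed by it. Under 3.5 item 3 only non-safety misses are replaced, so a DLT subject removed for a safety-related miss is not replaced.

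Reported rate = (D − d) / (6 − d − k)

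| D | d | k | Primary table | All 6 dosed |
|---|---|---|---|---|
| 1 | 1 | 0 | 0/5 = 0% | 1/6 = 17% |
| 2 | 0 | 0 | 2/6 = 33% | 2/6 = 33% |
| 2 | 1 | 0 | 1/5 = 20% | 2/6 = 33% |
| 2 | 1 | 1 | 1/4 = 25% | 2/6 = 33% |
| 2 | 1 | 2 | 1/3 = 33% | 2/6 = 33% |
| 2 | 0 | 1 | 2/5 = 40% | 2/6 = 33% |

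With D = 1 and d = 1 the rate is 0 for any k. In the fifth row the percentage is unchanged, but one DLT is still missing.

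**Direction in general.** With true rate p, and shares f of DLT and g of non-DLT subjects removed:

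Reported rate = p(1 − f) / [p(1 − f) + (1 − p)(1 − g)]

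This is below p only when f > g. Taking p = 1/3 and f = 0.25, so that p(1 − f) = 0.25:

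- g = 0: 0.25/(0.25 + 0.667) = 0.273
- g = 0.10: 0.25/(0.25 + 0.600) = 0.294
- g = 0.25: 0.25/(0.25 + 0.500) = 0.333
- g = 0.40: 0.25/(0.25 + 0.400) = 0.385

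The values of p, f and g are assumptions used only to show direction; the documents give none of them.

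**The case against.** The best defence is that the definition opens with subjects whose tolerability was assessed, which fits a subject with a confirmed DLT, and that 3.5 item 3 is the specific exclusion rule and spares safety-related misses. On that view the passages are merely in tension. The parenthesis, however, says who the assessed subjects are. The protocol's Definitions of Terms also ties being evaluable for DLT to receiving the Course 1 drug and completing examinations. Section 3.5 shows that an exception was probably intended; it does not put one in the analysis set.

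SAP section 4 provides for confirming which subjects are included before the final analysis, and with at most 24 subjects an excluded DLT would probably be noticed. That step supplies no rule, and in an open-label trial it leaves the decision to people who know the outcome.

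Several points do stand:

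- The route is narrow. Discretionary skipping of doses is expressly allowed only from Course 2 (3.5 item 5), although 8.3.5 lists interruption as a possible action after any AE.
- DLTs are also tabulated on all treated subjects, exclusions and Course 1 dose counts are displayed (SAP 7.2 and 9.1), and no tests or intervals are planned (SAP 6.5).
- The safety-set denominator is everyone dosed, so it can exceed 6 if subjects were replaced.
- Timing matters. The SAP is based on the protocol version of 13 Oct 2017, after the 25 Aug 2017 lock date it gives for Cohorts 1, 2 and 4.

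These limit the consequence and add to the cost of a change. They do not make the rule right.

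**Conclusion.** The concern holds: the set definition is wrong as written, and should be fixed. Followed literally, it removes a subject whose DLT costs a Course 1 dose or scheduled assessment from the only primary endpoint table. It conflicts with Protocol 3.5 item 3 by clear implication rather than by express contradiction.

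The loss of one such subject is a matter of counting and needs no assumption about rates. How often it would happen cannot be derived from the documents, so no probability is attached. The net direction of the percentage is not fixed either, because non-DLT subjects can be removed by the same rule. What is fixed is that a DLT can be lost and none added. Nothing here shows a changed escalation decision, a changed MTD or a risk to subjects, because the escalation rule counts subjects in the cohort and does not refer to this set.

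**What to change.** In Protocol 11.1.1.1 and SAP 5.1.1.1, define the DLT analysis set as dosed subjects who either:

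- (a) had a DLT in the DLT evaluation period, whatever doses or assessments were completed; or
- (b) had no DLT, received all scheduled doses and completed all assessments of that period.

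Then reconcile the definition with Protocol 3.5 item 3. The sponsor must state how subjects without a DLT who are cut short for safety reasons are counted, since item 3 by implication keeps them and limb (b) alone would not. With 2 DLTs in 6 and one such subject, the rate is 2/6 (33%) if kept and 2/5 (40%) if excluded. The text should also cover a subject who has a DLT and separately misses something for a non-safety reason, whom limb (a) keeps and item 3 excludes.

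The cost is a short amendment to each document and no extra data. Protocol 11.4 requires the timing and reason for an SAP change to be reported in the CSR, which matters here because of the lock date for Cohorts 1, 2 and 4. The reported rate may be less favourable, for example 2/6 (33%) where the present rule would show 1/5 (20%).
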